2.1 Background & Aims

Femoral neck fractures are a significant source of morbidity and mortality among the aged population. Due in large part to prolonged immobilization and related systemic consequences. Hip fractures among the elderly have increased dramatically worldwide, from 1.7 million in 1990 to an anticipated 6.3 million in 2050. Immobilization following a fracture frequently leads to decreased inspiratory capacity, compromised pulmonary mechanics and altered cardiovascular regulation, which raises the risk of pneumonia, hypertension and delayed functional recovery. Early cardiopulmonary rehabilitation during the immobilization phase is crucial since respiratory infections and cardiovascular problems have been found to be major causes of early mortality after hip fractures.

Due to medical comorbidities and logistical limitations, prolonged bed rest and delays in surgical intervention are still typical in older patients despite advancements in surgical management. These elements worsen hemodynamic instability and pulmonary deconditioning. While respiratory and cardiovascular components receive less attention during early immobility, musculoskeletal recovery is frequently given priority in conventional therapy.

Breathing-based therapies provide a practical and affordable way to deal with these issues. In patients with chronic respiratory diseases, Liuzijue Qigong, a traditional Chinese breathing practice that combines controlled expiration with sound vibration, has been shown to improve lung function, respiratory muscle efficiency and overall quality of life. In a similar vein, Box Breathing is an organized breathing method that has been demonstrated to improve blood pressure control, autonomic balance and lung volumes.

In cardiopulmonary rehabilitation, breathing-based therapies have become more popular because of their ease of use, affordability and viability for older people who are fragile and immobile. Respiratory

efficiency and hemodynamic stability can be enhanced by methods like Box Breathing and Liuzijue Qigong, which are known to affect autonomic regulation, respiratory muscle function and cardiovascular responses. These treatments are especially important for older patients who have suffered femur neck fractures since prolonged immobility frequently results in decreased lung volumes, decreased inspiratory capacity and altered blood pressure control.

Comparative research assessing the efficacy of these breathing methods in elderly individuals immobilized after femur neck fractures is, however, lacking. Furthermore, only a few studies have used objective measurement instruments like volume-oriented incentive spirometry to look at their combined effects on blood pressure and inspiratory capacity. By methodically contrasting Box Breathing with Liuzijue Qigong, this randomized controlled experiment seeks to close this evidence gap and advance evidence-based cardiopulmonary rehabilitation techniques for this susceptible group.

2.2 Background Literature Review

Femoral neck fractures are a major contributor to morbidity and mortality among older adults, particularly due to prolonged immobilization and associated systemic complications. In a three-year follow-up study, **Berggren et al. (2016)** reported a high prevalence of cardiovascular, respiratory, and metabolic comorbidities in individuals with femoral neck fractures, with complications during immobilization significantly contributing to mortality. The authors emphasized the necessity of early supportive interventions to reduce secondary physiological decline and improve survival outcomes ⁽¹⁾.

Expanding on fracture-related risks, **Gouzoulis et al. (2025)** analyzed the incidence and contributing factors of femoral neck fractures and subsequent surgical outcomes. Their findings indicated that advanced age, prolonged inactivity, and compromised cardiopulmonary reserve adversely affect recovery and increase postoperative complications. The study highlights the importance of adjunctive non-

pharmacological strategies to optimize cardiopulmonary function during the immobilization period ⁽²⁾.

Mind–body interventions have shown promise in addressing respiratory dysfunction in older populations.

Feng et al. (2020) evaluated the role of Qigong practices in elderly individuals and demonstrated improvements in respiratory efficiency, autonomic regulation, and psychological well-being. Although conducted in the context of COVID-19 rehabilitation, the study supports the applicability of Qigong-based exercises, such as Liuzijue, in enhancing inspiratory capacity in populations with restricted mobility ⁽³⁾.

Further evidence is provided by **Xu et al. (2022)** through a systematic review and meta-analysis examining the efficacy of Liuzijue Qigong in patients with chronic obstructive pulmonary disease. The analysis revealed significant improvements in inspiratory capacity, pulmonary function, and exercise tolerance, confirming Liuzijue as a safe and effective respiratory rehabilitation modality suitable for elderly individuals with limited physical capacity ⁽⁴⁾.

Breathing-focused interventions have also demonstrated cardiovascular benefits. In a randomized controlled trial, **Zaliene et al. (2025)** reported that structured breathing techniques significantly improved autonomic balance, respiratory efficiency, and stress regulation. Notably, reductions in blood pressure and enhanced parasympathetic activity were observed, supporting the clinical relevance of Box Breathing in managing cardiovascular strain associated with immobilization ⁽⁵⁾.

Collectively, existing literature supports the use of Liuzijue Qigong and Box Breathing techniques in improving respiratory and cardiovascular parameters in elderly populations. However, comparative evidence assessing their effectiveness specifically in patients following femoral neck fracture immobilization remains limited, warranting further investigation.

3. Study Protocol

3.1 Research Design Outline

The study aims to perform a Comparative study on older people who have been immobilized due to femur neck fractures.in Saveetha Medical College and Hospital.

Formerly titled “Effectiveness of Liuzijue and Box Breathing Techniques on Inspiratory Capacity and Blood Pressure Following Femoral Neck Fracture Immobilization: A Retrospective Comparative Study” involves elderly with femoral neck fracture immobilization by Inspiratory capacity and blood pressure were assessed using a volumetric incentive spirometer and a digital sphygmomanometer, respectively. Improvement in inspiratory capacity was defined as an increase in measured values, with ranges progressing from approximately 1300 mL to 3000 mL. Improvement in cardiovascular status was considered when blood pressure remained within a stable range, with systolic values between 120-150 mmHg and diastolic values between 70-90 mmHg.

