3.3 Recruitment

For this retrospective analysis, medical and physiotherapy records of patients with femoral neck fracture immobilization treated at the Saveetha Medical College and Hospital were reviewed.

Records of participants who had completed a four-week intervention program and had documented outcome measures were included in the study. No direct recruitment or prospective enrollment was undertaken.

Data related to inspiratory capacity measured using a volumetric spirometer and blood pressure assessed using a digital sphygmomanometer were extracted from patient records. Outcome measures recorded at baseline (pre-intervention), at the second week and at the fourth week were included for analysis. Confidentiality of patient information was maintained and the study procedures were conducted under the approval and supervision of the institutional ethics committee and the principal investigator.

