3.5.2 Secondary outcomes

- Blood Pressure - Digital Blood Pressure Monitor (Digital Sphygmomanometer)
 - To measure systolic and diastolic blood pressure. To evaluate cardiovascular response to breathing interventions. To monitor physiological changes over the intervention period
 - Automated, non-invasive device using Oscillo metric methods.
 - Consists of inflatable cuff and digital display.
 - Blood pressure recorded after adequate rest

4. Statistical Analysis Plan (SAP)

Descriptive and inferential statistics will be used. Normally distributed data will be presented by mean and standard deviation (SD) and non-normally distributed data will be presented by median and interquartile range. Categorical data will be presented using percentages. SPSS (version 27.0) will be used for all statistical analyses.

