4.1 Primary Outcomes

Statistical analysis will be performed using appropriate statistical software. Descriptive statistics, including mean and standard deviation, will be calculated for the primary outcome variables: Inspiratory capacity (mL) for both intervention groups.

To evaluate changes over time and differences between groups, a mixed-design repeated measures analysis of variance (ANOVA) will be used, with time (baseline, 2nd week, and 4th week) as the within-subject factor and group (Liuzijue Qi Gong exercise and Box Breathing technique) as the between-subject factor. This analysis will determine the effectiveness of the interventions across the different time intervals.

Post-hoc pairwise comparisons with Bonferroni correction will be conducted when significant main effects or interactions are observed. Mauchly's test of sphericity will be applied, and if the assumption of sphericity is violated ($p < 0.05$), the Greenhouse-Geisser correction will be used. A p -value < 0.05 will be considered statistically significant.

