4.2 Secondary Outcomes

Secondary outcome analysis will include systolic and diastolic blood pressure parameters to assess cardiovascular responses to the interventions. Descriptive statistics (mean \pm standard deviation) will be computed for each time point within and between groups.

A repeated measures ANOVA will be performed to examine within-group changes across time and between-group differences in blood pressure values. Where significant effects are identified, post-hoc analysis with Bonferroni adjustment will be carried out to explore pairwise differences between baseline, 2nd week, and 4th week measurements. In cases of sphericity violation, the Greenhouse-Geisser correction will be applied. Statistical significance will be set at $p < 0.05$.

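### Section 3.1 counts in-range blood pressure as an improvement; that is a status, and it is not what section 4.2 analyses

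*Combined protocol and SAP*

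**What the plan says.** Section 3.1 gives the only criterion for blood pressure improvement in the document: "Improvement in cardiovascular status was considered when blood pressure remained within a stable range, with systolic values between 120-150 mmHg". The full limits are "systolic values between 120-150 mmHg and diastolic values between 70-90 mmHg". The sentence before it deals with the primary outcome: "Improvement in inspiratory capacity was defined as an increase in measured values".

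Section 3.3 sets the visits: "Outcome measures recorded at baseline (pre-intervention), at the second week and at the fourth week were included for analysis". Section 3.5.2 makes blood pressure a secondary outcome, and one of its stated purposes is "To monitor physiological changes over the intervention period".

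Section 4.2 plans means and SDs at each visit and then the inferential step: "A repeated measures ANOVA will be performed to examine within-group changes across time and between-group differences in blood pressure values". Bonferroni-adjusted comparisons between visits follow if an effect is significant. The section contains no in-range indicator, no proportion of patients improved and no statement of which direction of change is favourable. The opening of section 4 says that categorical data will be shown as percentages, but it names no blood pressure category.

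**The concern.** The rule in 3.1 attaches the word improvement to a position within limits. It names no comparison with baseline, no direction and no amount of change. The analysis in 4.2 is about change over time and differences between groups in mmHg. The two can therefore give different answers, and the plan does not say which one governs the conclusion.

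What is at stake is the conclusion. An author following 3.1 could report that cardiovascular status improved in one or both groups when mean pressure did not move and the groups did not differ. The records already exist (sections 3.2 and 3.3), so a rule that leaves its visits open could also be settled after the values have been seen.

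**Working it through.** **1. Apply the stated limits to example patients.** The limits come from 3.1 and the visits from 3.3; the patients are hypothetical. Both components are taken to be required, and where baseline and week 4 are both in range, week 2 is taken to be in range too.

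| Baseline | Week 4 | Change (mmHg) | Baseline in range? | Week 4 in range? | Under 3.1 |
|---|---|---|---|---|---|
| 130/80 | 130/80 | 0/0 | yes | yes | improved |
| 122/72 | 149/89 | +27/+17 | yes | yes | improved |
| 170/95 | 151/88 | -19/-7 | no | no (151 > 150) | not improved |
| 170/95 | 140/85 | -30/-10 | no | yes | undetermined |

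The last row turns on the verb 'remained'. If only week 4 counts, the patient is improved. If baseline must also be in range, the patient is not. The plan does not say.

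**2. Compare with the analysis.** Sections 3.5.2 and 4.2 agree with each other: blood pressure is a measured value followed over time. Neither refers to the limits. The conflict is confined to the one sentence in 3.1.

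**3. Illustrate how the two can disagree.** The documents give no blood pressure mean, SD or correlation, so there is no plan figure to reproduce, and every mean and SD here is an assumption. Section 2.1 says that immobilisation affects cardiovascular regulation, "which raises the risk of pneumonia, hypertension and delayed functional recovery", but gives no values. For normally distributed systolic pressure at a single visit with mean m and SD s:

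Share in range = Φ((150 − m)/s) − Φ((120 − m)/s)

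The midpoint is (120 + 150)/2 = 135, so two means equally far from 135 give the same share. Means of 125 and 145 are each 10 mmHg away:

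- s = 10: Φ(0.5) − Φ(−2.5) = 68.5% for both means
- s = 15: Φ(0.33) − Φ(−1.67) = 58.3% for both
- s = 20: Φ(0.25) − Φ(−1.25) = 49.3% for both

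A 20 mmHg difference in means, which is what the ANOVA addresses, leaves the share unchanged. With s = 15, the same 10 mmHg fall in the mean can move the share either way or not at all:

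- 150 to 140: 47.7% to 65.6% (rises)
- 140 to 130: 65.6% to 65.6% (no change)
- 130 to 120: 65.6% to 47.7% (falls; the mirror image of the first line about 135)

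The share and the mean are related but not interchangeable.

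**4. Check which term in 4.2 would carry the conclusion.** Section 4.1 specifies a mixed design with time and group as factors and follows up either kind of effect: "Post-hoc pairwise comparisons with Bonferroni correction will be conducted when significant main effects or interactions are observed". Section 4.2 names no term. A group main effect averages all visits, baseline included. Suppose the groups are equal at baseline and differ by D/2 at week 2 and D at week 4. The main effect is then (0 + D/2 + D)/3 = D/2. A constant gap B present from baseline would enter the main effect in full, (B + B + B)/3 = B, but cancels from change from baseline. The group-by-time interaction addresses differential change directly.

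**The case against.** **No planned analysis uses the rule.** This stands. Section 4.2 already reports values by visit and tests them, and the sentence in 3.1 is a loosely built, past-tense line in a design outline that may have been meant descriptively. A reader might infer that the ANOVA or its p-values are compromised; the documents do not support that. But the sentence is worded as a criterion, and it is the only one offered for blood pressure.

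**Staying within a range is a coherent aim.** This also stands. Section 2.1 names haemodynamic stability among the expected benefits, although 2.2 also cites reductions in blood pressure. A reader might infer that judging inspiratory capacity by change and blood pressure by status is itself an error. It is not, because the two outcomes may reasonably have different aims. What remains is narrower: staying in range is maintenance, not improvement, and the visits are not stated.

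**The interaction is a separate matter.** Partly so: it does not follow from the wording of 3.1. But once the rule is removed, 4.2 alone carries the conclusion, so it should say which term answers the between-group question.

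**The in-range status could instead be specified in full and analysed as a binary outcome.** That would also reconcile the sections, but it adds an endpoint and several choices (visits, components, patients out of range at baseline) that 4.2 does not need.

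**Conclusion.** The point holds and should be acted on; its weight is moderate because blood pressure is a secondary outcome. It rests on the text alone: the 3.1 rule is an in-range status, sections 3.5.2 and 4.2 concern measured values and change, and nothing connects them. The example patients show the problem without any distributional assumption.

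Its numerical size in this study cannot be derived. The normal-distribution figures show only that disagreement is possible, for systolic pressure at one visit under assumed means and SDs. A reader might infer from them a particular proportion of misclassified patients, or a usual direction of error; with no blood pressure inputs in the documents, neither is supported. Nothing here judges whether the mmHg limits are clinically right.

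**What to change.** Reconcile 3.1 with 3.5.2 and 4.2:

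- Delete the blood pressure improvement rule from 3.1 and state that the blood pressure conclusion rests on the 4.2 analysis of systolic and diastolic values.
- Add to 4.2 that, as in the mixed design of 4.1, the between-group comparison is read from the group-by-time interaction and reported as the difference between groups in change from baseline, at weeks 2 and 4, with 95% CI.
- If in-range status is kept, report it descriptively with the sponsor's existing limits, by group and by baseline in-range status, at stated visits. Label patients in range throughout as 'maintained', not 'improved'. No further test is needed.

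The cost is one sentence removed, one added and, if wanted, one small table from data already being extracted. The downside for the sponsor is a possibly less favourable statement about blood pressure.

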3.2 Participants

This retrospective study included elderly individuals diagnosed with femoral neck fracture who had undergone a period of immobilization and subsequently received either Liuzijue Qi Gong exercise or Box Breathing technique as part of their rehabilitation program. Participants were identified through a review of medical and physiotherapy records from Saveetha Medical College and Hospital. Eligibility was determined based on inclusion and exclusion criteria documented in the clinical records.

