3.5 Assessment & Outcomes Measures

3.5.1 Primary outcomes

- Inspiratory Capacity -Volume-Oriented Incentive Spirometer
 - To measure inspiratory capacity in elderly participants, post femoral neck fracture immobilization. To objectively monitor changes in pulmonary function.
 - Instructed to inhale slowly and deeply through the mouthpiece after normal expiration.
 - Maximum volume achieved recorded as inspiratory capacity.

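### Change over time in inspiratory capacity cannot be credited to either breathing technique, because each was given inside an undescribed rehabilitation programme, no co-treatment is named for extraction, and there is no untreated group

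*Combined protocol and SAP*

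**What the plan says.** Section 3.2 states that patients received one technique or the other "as part of their rehabilitation program". The table in Section 3.4 specifies the two techniques and nothing else in the programme.

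Section 3.3 describes a records review: "No direct recruitment or prospective enrollment was undertaken". On data, it says: "Data related to inspiratory capacity measured using a volumetric spirometer and blood pressure assessed using a digital sphygmomanometer were extracted from patient records". The time points are baseline, week 2 and week 4. No co-treatment item is named.

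The primary outcome in Section 3.5.1 is headed "Inspiratory Capacity -Volume-Oriented Incentive Spirometer", and the rule for the value is "Maximum volume achieved recorded as inspiratory capacity".

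Section 4.1 specifies a mixed-design ANOVA with time as the within-subject factor and "group (Liuzijue Qi Gong exercise and Box Breathing technique) as the between-subject factor". It lists no covariate. Its stated inference is: "This analysis will determine the effectiveness of the interventions across the different time intervals". Section 4.2 uses the same kind of analysis for blood pressure.

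**The concern.** If a technique is one part of a programme, a rise in inspiratory capacity between baseline and week 4 is the result of everything that happened in those four weeks. Section 4.1 attributes it to the technique. Section 3.1 counts any increase as improvement, so a gain from another source would be reported as success.

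The choice of outcome adds to this. It is the best volume a patient reaches on a bedside device, so it depends on effort and can rise with familiarity. An incentive spirometer can also serve as an exercise device. A patient who used it that way would have been practising the outcome test.

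Two results are at stake, and they behave differently. The time effect is exposed even when both groups were treated alike, because no group went without a technique. The comparison between techniques is exposed, by this route, only if concurrent treatment was unequal. Adjusting for baseline characteristics would not by itself settle either, because the treatments in question come after baseline.

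**Working it through.** **1. Figure to reproduce.** There is none. The documents give no sample size, power, effect size or SD.

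**2. Text check.** I looked for any record of, restriction on, or adjustment for concurrent treatment.
- Sections 3.2 and 3.4: a wider programme exists and its other content is not described.
- Section 3.2: eligibility criteria are referred to but not listed, so no stated exclusion removes patients with co-treatment.
- Section 3.3: inspiratory capacity and blood pressure are the only data named.
- Section 4.1: time and group only, with two active groups.

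The closing paragraph of the background (2.1) calls the study randomised. Sections 3.1 to 3.3 describe a retrospective review of treatment already received, and I follow those.

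**3. What each term of the model contains.** For group g, let T_g be the technique effect, p_g the share of patients with a co-treatment, b its gain (taken as equal in both groups), R the repeat-test gain and H the natural recovery. Then

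mean change in group g = T_g + p_g × b + R + H.

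- Time effect: the average of this over groups. It contains all four parts.
- Group-by-time contrast: (T_L − T_B) + b × (p_L − p_B), with L for Liuzijue and B for Box Breathing. R cancels if retest practice is similar, since both groups have the same assessment points (3.4). H cancels if recovery is similar. Co-treatment drops out when p_L = p_B.

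**4. Illustrative size.** Every input here except the 5% level is an assumption, and the test is taken as two-sided because 4.1 does not say. SD of change is 300 mL, n is 20 to 50 per group, and T_L = T_B = 0. I use a normal test on baseline to week-4 change as a stand-in for the ANOVA:

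P(significant) = Φ(δ/SE − 1.96) + Φ(−δ/SE − 1.96).

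The SE between groups is 300 × √(2/n): 94.9 mL at n = 20 and 60 mL at n = 50. The SE of the pooled change is 300/√(2n): 47.4 mL at n = 20 and 30 mL at n = 50.

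| Result | Assumed gain b | Assumed use | False shift δ | P(significant), n = 20 to 50 |
|---|---|---|---|---|
| Between groups | any | equal | 0 mL | 5% |
| Between groups | 100 mL | 10 points apart | 0.10 × 100 = 10 mL | 5.1% to 5.3% |
| Between groups | 300 mL | 30 points apart | 0.30 × 300 = 90 mL | 16% to 32% |
| Time effect | 200 mL | half of each group | 0.50 × 200 = 100 mL | 56% to 92% |
| Time effect | 200 mL | all patients | 200 mL | 99% to 100% |

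Worked example, time effect with δ = 100 mL: 100/47.4 = 2.11, and Φ(2.11 − 1.96) is about 0.56. At n = 50, 100/30 = 3.33, and Φ(3.33 − 1.96) is about 0.92.

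The time effect needs no imbalance to mislead. The between-group effect ranges from negligible to material, depending on inputs that the documents do not supply.

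**The case against.** The strongest reply is that the documents describe the spirometer only as a measuring instrument (2.1, 3.1 and 3.5.1). Nothing says that a patient exercised with it or had other chest physiotherapy. The only remark on usual care, in 2.1, is that breathing and circulation get less attention than musculoskeletal recovery in early immobility. That is general background rather than an account of this hospital, but it points away from widespread respiratory co-treatment. This objection stands. A reader might infer that spirometer training produced the primary result, and the documents do not support that.

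Second, the study compares two active techniques, and equal co-treatment with a similar gain leaves that comparison intact. This also stands. A reader might infer that the comparison is biased towards one technique, but that needs unequal use, of which there is no evidence. What remains is that treatment was not randomised and nothing in the plan would reveal an imbalance.

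Third, Section 3.3 does not claim to be a complete field list. That is fair: the supportable statement is that no co-treatment is named for extraction, not that none will be collected.

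Fourth, an analysis restricted to patients without therapeutic spirometer use selects on something that happened after baseline and may depend on early response or deterioration. It can add selection bias, and agreement with the main result would not exclude mobilisation, other physiotherapy or natural recovery. This stands, and the fix does not rely on such an analysis.

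None of these replies answers the point on the time effect. With no untreated group, it cannot be read as effectiveness of a technique.

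**Conclusion.** The concern holds in a limited form. Change over time in inspiratory capacity cannot be separated from the rest of the programme, repeat-test practice or natural recovery, so the inference stated in Section 4.1 is not supported for within-group change. The same reasoning applies to blood pressure in 4.2, apart from the practice element, which is specific to the spirometer. This part rests on the text alone.

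The contrast between techniques is at risk by this route only if co-treatment differed between the groups. Whether it did is unknown, and the plan as written names no data that would show it. All the millilitre figures and error rates above are assumptions. They show how the bias scales and do not estimate it for this study.

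**What to change.** 1. **Sections 4.1 and 4.2.** Draw the comparative conclusion from the group-by-time interaction only. The group main effect averages over all three time points, including baseline, so it does not isolate differential change. Report within-group change as change under a rehabilitation programme that contained each technique, not as effectiveness of the technique. Keep this wording whatever the sensitivity analysis shows.
2. **Section 3.3.** Add to the extraction, from baseline to week 4, therapeutic use of the incentive spirometer, other chest physiotherapy, and mobilisation. Tabulate them by technique.
3. **Section 4.1.** If these differ between groups, add a sensitivity analysis of week-4 inspiratory capacity adjusted for baseline and co-treatment. Label it exploratory, because co-treatment is post-baseline and may depend on early response. Do not let agreement in a restricted subset restore the attribution to the technique.
4. If the notes lack these data, state that as a limitation.

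The cost is a few extra fields from physiotherapy notes already under review, one conditional analysis, and a change of wording. The notes may be incomplete for some patients. The wording change is needed in any case and costs nothing.
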